## 1. INTRODUCTION

The purpose of this Statistical Analysis Plan (SAP) is to describe the analyses to be included in the Clinical Study Report for Protocol HBMS01.

## 2. SUMMARY OF KEY PROTOCOL INFORMATION

### 2.1. Study Objective(s), Estimand(s) and Endpoint(s)

Objectives	Endpoints
Primary Objective	Primary Endpoint

To investigate the efficacy of intravenous infusions of HB-adMSCs vs Placebo in patients with Multiple Sclerosis as determined by improvements in Multiple Sclerosis Quality of Life (MSQOL)-54 Instrument. (Time frame: Baseline to Week 52).

	

Changes from Baseline at Weeks 52 in Multiple Sclerosis Quality of Life (MSQOL)-54 Instrument scores following treatment with HB- adMSCs or Placebo. This 54-item questionnaire provides 12 subscales, two summary scores, and two extra single-item measures. The subscales are physical function, role limits-physical, emotional role restrictions, pain, emotional well-being, energy, health perceptions, social function, cognitive function, health distress, overall quality of life, and sexual function.

Secondary Objective	Secondary Endpoint

To evaluate the efficacy of intravenous infusions of HB-adMSCs vs. Placebo in patients with Multiple Sclerosis as determined by changes in Expanded Disability Status Scale (EDSS) (Time frame: Baseline to Week 52).

To assess the efficacy of intravenous infusions of HB-adMSCs vs. Placebo in patients with Multiple Sclerosis as determined by changes in The Barthel Index (Time frame: Baseline to Week 52).

To determine the efficacy of intravenous infusions of HB-adMSCs vs. Placebo in patients with Multiple Sclerosis as determined by changes in 9-Hole Peg Test (Time frame: Baseline to Week 52).

	

Change from baseline at Week 52 in Total Expanded Disability Status Scale (EDSS) scores following treatment with HB- adMSCs or Placebo

Change from baseline at Week 52 in Barthel Index scores following treatment with HB- adMSCs or Placebo

Change from baseline at Week 52 in 9-Hole Peg Test scores following treatment with HB- adMSCs or Placebo

Objectives	Endpoints


• To identify the safety of intravenous infusions of HB-adMSCs vs. Placebo in patients with Multiple Sclerosis as determined by changes in Patient Health Questionnaire (PHQ-9) (Time frame: Baseline to Week 52).

• To assess the safety of intravenous infusions of HB-adMSCs vs. Placebo in patients with Multiple Sclerosis as determined by the incidence of adverse events or serious adverse events (Time frame: Baseline to Week 52).

	

• Change from baseline at Week 52 in Patient Health Questionnaire (PHQ-9) scores following treatment with HB-adMSCs or Placebo

• Incidence of treatment-emergent Adverse Event (TEAEs) and serious Adverse Events (SAEs)

• Incidence and risk of AEs of special interest (serious or nonserious), including thromboembolic events, peripheral events defined as, thromboembolism of the extremities, also infections and hypersensitivities.

• Clinically significant changes in laboratory values, vital signs, weight, physical examination results and Multiple Sclerosis concomitant medications.

## 2.2. Study Design

Overview of Study Design and Key Features	
	<pre> graph TD     Screening[Screening] --> Eligible{Eligible}     Eligible -- No --> ScreeningFailure[Screening Failure]     Eligible -- Yes --> Randomization[Randomization]     Randomization --> Week0[Week 0 (Baseline)]     Week0 --> Week4[Week 4 INF # 2]     Week4 --> Week8[Week 8 INF # 3]     Week8 --> Week16[Week 16 INF # 4]     Week16 --> Week24[Week 24 INF # 5]     Week24 --> Week32[Week 32 INF # 6]     Week32 --> Week42[Week 42 Follow Up]     Week42 --> Week52[Week 52 EOS]   </pre>
Design Features	
This study will be a randomized, double-blind, single center, phase 2 study to assess efficacy and safety of multiple HB-adMSCs vs. Placebo for the treatment of Multiple Sclerosis. The trial includes,
 
 
• A screening period of up to 4 weeks
 
• A 32-week treatment period while on randomized study treatment 
 
▪ Infusion 1 (Week 0), Infusion 2 (Week 4), Infusion 3 (Week 8), Infusion 4 (Week 16), Infusion 5 (Week 24) and Infusion 6 (Week 32)
 
 
 
• A safety Follow-up period of 20 weeks after the last investigational product administration. 
 
▪ Follow up at week 42 and end of study at Week 52
 
 
 
• 24 Subjects
 
• 2 Treatment groups 
 
▪ Group 1 → HB-adMSCs
 
▪ Group 2 → Placebo
 
 
 

Study Intervention	
 
• Active Product: HB- adMSCs (Hope Biosciences adipose derived mesenchymal stem cells) 
 
▪ Dose: 200 million
 
▪ Route: Intravenous
 
▪ Regimen: Weeks 0, 4, 8, 16, 24 and 32.
 
 
 
• Placebo: Saline Solution 0.9% 
 
▪ Dose: N/A
 
▪ Route: Intravenous
 
▪ Regimen: Weeks 0, 4, 8, 16, 24 and 32.
 
 
 
• Duration of administration 1 hour
 
• Study treatment details,
 

Overview of Study Design and Key Features		
	<pre> graph TD     subgraph Placebo_Path [Placebo]         direction TB         M[Manufacturer] --- BE[Baxter or an equivalent manufacturer]         BE --- D[20 ml sterile saline]         D --- R[Intravenous]         R --- AR[4-5 ml/min]         AR --- P[Preparation]         P --- PS[Placebo will contain 20 ml of sterile saline. Placebo should be diluted in 250 ml of 0.9% Sodium chloride.]     end      subgraph HBadMSCs_Path [HB-adMSCs (autologous)]         direction TB         H[Hope Biosciences] --- D2[2 x 10^8 ± 20% cells suspended in 20 ml sterile saline]         D2 --- R2[Intravenous]         R2 --- AR2[4-5 ml/min]         AR2 --- P2[Preparation]         P2 --- PS2[Syringe will contain 20 ml of autologous HB-adMSCs. HB-adMSCs should be diluted in 250 ml of 0.9% Sodium chloride.]     end </pre>	
Study Intervention Assignment	
 
Participants will be randomised 1:1 to receive HB-adMSCs active treatment or Placebo.
 
	
Interim Analysis	
 
No interim analysis will be performed in this study
 
	

### 3. STATISTICAL HYPOTHESES

The primary analysis will test whether HB-adMSCs is superior to Placebo according to the following statistical hypotheses:

**Null hypothesis H0:** The difference in change from baseline at Weeks 52 in Multiple Sclerosis Quality of Life (MSQOL)-54 Instrument scores between treatment groups (HB-adMSCs – Placebo) is equal to zero.

**Alternative hypothesis H1:** The difference in change from baseline at Weeks 52 in Multiple Sclerosis Quality of Life (MSQOL)-54 Instrument scores between treatment groups (HB-adMSCs – Placebo) is not equal to zero.

Secondary analysis will be tested for mean difference for change from Baseline to Week 52 for efficacy endpoints for both treatment groups,

**Null hypothesis H0:**  $\Delta = 0$

**Alternative hypothesis H1:**  $\Delta \neq 0$

### 3.1. Multiplicity Adjustment

The Bonferroni-Holm method for adjustment of multiplicity adjustment is performed for all secondary efficacy endpoint of interest.

Bonferroni-Holm method starts with ordering the p-values in increasing order and starts with testing the hypothesis with the lowest p-value on the  $5/k\%$  level (two-sided), where  $k$  is the number of hypotheses in the procedure. If significant, the testing proceeds to comparing the next lowest p-value with  $5/(k-1)\%$ .

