A repeat measure mixed model will be used to assess within-subject changes from baseline. correction for multiple comparisons will be employed for post-hoc comparisons. Multiple Sclerosis's assessment scores (i.e., MSQOL) at screening and infusion 1 (before treatment) will be averaged and treated as a baseline. Averaging is performed to minimize sources of variance (i.e., patient condition, assessors) and particularly to establish a reliable baseline from which to establish changes.

Data Handling

Case Report Forms (CRF)

As used in this protocol, the term CRF should be understood to refer to either a paper form or an electronic data record or both. Reports received by the site, or from the central laboratory should be printed, retained as source documentation, and signed by the principal investigator, indicating which values are considered clinically significant and to be reported as AEs if applicable.

The completion, review, and approval of all CRFs, as well as the completeness and authenticity of all clinical and laboratory data entered on these CRFs, are always the PI's personal responsibility. Signature of Principal Investigator will be required to attest that the information contained on the CRFs is accurate.

Original CRFs should not be made available in any form to third parties, except for authorized representatives of Hope Biosciences Stem Cell Research Foundation or appropriate regulatory authorities, without written permission from Hope Biosciences Stem Cell Research Foundation.

Changes in the Conduct of the Clinical Trial

Protocol Amendments

Any change to the protocol will need to have a protocol amendment submitted to the IND, and FDA and IRB must agree prior to proceeding.

Premature Clinical Trial Termination

Both the Study Investigator and Sponsor have the right to terminate the clinical trial at any time. Should this become necessary, the procedures will be agreed upon after consultation between the two parties. In terminating the clinical trial, the Sponsor and the Study Investigator will ensure that adequate consideration is given to the protection of the best interests of the study participants. Regulatory authorities and IRB will be informed.

In addition, the Sponsor reserves the right to terminate the participation of any clinical trial site. Conditions that may warrant termination include, but are not limited to:

- Insufficient adherence to protocol requirements
- Failure to enter patients at an acceptable rate

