#### 5.1.1. General Methodology

Unless otherwise stated, all hypotheses will be tested at a 2-sided significance level of 0.05 and 95% confidence interval. All continuous measurements will be summarised descriptively at each visit by treatment using observed data.

Summary of continuous variables will be presented using N, Mean, 95% confidence interval of mean, Standard Error of mean (SE), Standard Deviation (SD), Median and Range (Minimum and Maximum). The categorical variables will be presented using number and percentage based on N.

For measurements over time mean values will be plotted to explore the trajectory over time. Observed data will be used as the basis for plotting data along with bars as +/- SE, not otherwise specified.

As a primary analysis, a standard Analysis of Covariance (ANCOVA) will be applied for primary and secondary endpoint to test the significance of the effects of the treatment at Week 52. The model includes treatment as fixed factor and the corresponding baseline value as a covariate.

A parametric Repeated Measures Analysis (RMA) Model will be applied as a secondary analysis to test the significance of the effects of the treatment at Week 4, Week 8, Week 16, Week 24, Week 32, Week 42 and Week 52 including baseline as covariate.

Presentation of results from a statistical analysis model will include the estimated mean treatment effects (Least Square Means (LSMeans)). For all endpoints analysed statistically, estimated mean treatment differences will be presented together with two-sided 95% confidence intervals and p-values,

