#### 5.2.2. Main analytical approach

Primary analysis
Endpoint/Variables

 
Change from baseline at Weeks 52 in Multiple Sclerosis Quality of Life (MSQOL)-54 Composite scores following treatment with HB-adMSCs or Placebo.
 

ANCOVA Model Specification

 
To compare the HB-adMSCs to Placebo on Change from baseline to Week 52, a standard Analysis of Covariance (ANCOVA) model will be fitted
 
Terms fitted in the mixed effect model will include: 
 
Primary endpoint efficacy measurements available at - Week 52 will be response variable in a linear mixed model using a variance-covariance residual matrix.
 
The model will include: 
 
Fixed factors: treatment
 
Fixed stratification factors: Multiple's sclerosis severity (Mild disability (EDSS < 4) ; Moderate disability (EDSS > 4 and < 6.5)), Age (< 55 ; > 55) and Gender (Female ; Male)
 
 
 
 
 

• Covariate: baseline

Model Checking and Diagnostics
For the ANCOVA Model assumptions will be checked, and appropriate adjustments may be applied based on the data.
Distribution assumptions underlying the model used for analysis will be examined by obtaining a normal probability plot of the residual and a plot of the residuals versus the fitted values (i.e., checking the normality assumption and constant variance assumption of the model respectively) to gain confidence that the model assumptions are reasonable.
Non-parametric analyses, Mann-Whitney U (or Wilcoxon Rank-Sum) Test will be conducted if the normality assumptions do not hold.
Results presentation
Presentation of results from a statistical analysis model will include the estimated mean treatment effects (Least Square Means (LSMeans)) and estimated mean treatment differences will be presented together with two-sided 95% confidence intervals standard error for mean difference and p-value.
Secondary analysis
Endpoint/Variables
Change from baseline in Multiple Sclerosis Quality of Life (MSQOL)-54 Composite scores following treatment with HB-adMSCs or Placebo at Week 4, Week 8, Week 16, Week 24, Week 32, Week 42 and Week 52.
Repeated Measures Model Specification

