## **5.3. Secondary Endpoint(s) Analyses**

### **5.3.1. Efficacy Endpoints / Variables**

- Change from baseline at Week 52 in Total Expanded Disability Status Scale (EDSS) scores following treatment with HB- adMSCs or Placebo
- Change from baseline at Week 52 in Barthel Index scores following treatment with HB- adMSCs or Placebo
- Change from baseline at Week 52 in 9-Hole Peg Test scores following treatment with HB- adMSCs or Placebo
- Change from baseline at Week 52 in Patient Health Questionnaire (PHQ-9) scores following treatment with HB-adMSCs or Placebo

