#### **5.4. Changes to Protocol Defined Analyses**

Analysis is planned as per protocol. No deviation from the planned protocol specified analysis.

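### The SAP's only multiplicity correction leaves out the MSQOL-54 by-visit contrasts and paired tests, although the protocol foresees a correction for post-hoc comparisons and SAP 5.4 declares no change

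*SAP*

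**What the plan says.** **Protocol, Statistical Methods.** The analysis is introduced with "A repeat measure mixed model will be used to assess within-subject changes from baseline". The next sentence states that "correction for multiple comparisons will be employed for post-hoc comparisons". No method is named, and post-hoc is not defined. The same paragraph gives MSQOL as its example of an assessment score.

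**SAP 3.1.** The only multiplicity provision reads "The Bonferroni-Holm method for adjustment of multiplicity adjustment is performed for all secondary efficacy endpoint of interest". It describes the Holm steps ("If significant, the testing proceeds to comparing the next lowest p-value with" the next threshold) but gives k no number. SAP 5.3.1 lists four efficacy endpoints, beginning with "Change from baseline at Week 52 in Total Expanded Disability Status Scale (EDSS) scores following treatment with HB- adMSCs or Placebo", followed by the Barthel Index, 9-Hole Peg Test and PHQ-9. MSQOL-54 is the primary endpoint and is not on that list.

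**SAP 5.1.1 and 5.2.2.** The default is "Unless otherwise stated, all hypotheses will be tested at a 2-sided significance level of 0.05 and 95% confidence interval". The primary analysis of MSQOL-54 is an ANCOVA at Week 52. A secondary repeated-measures analysis with a treatment-by-visit interaction covers "Change from baseline in Multiple Sclerosis Quality of Life (MSQOL)-54 Composite scores following treatment with HB-adMSCs or Placebo at Week 4, Week 8" and so on to Week 52, and a p-value is to be presented with the treatment differences. An additional analysis applies paired t-tests from baseline to each visit, with a p-value shown for every post-baseline visit. No adjustment is mentioned for either set.

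**SAP 5.4.** "No deviation from the planned protocol specified analysis".

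**The concern.** A reader who holds the protocol would expect some correction for the follow-up comparisons from the repeated-measures model. The SAP corrects across the four secondary endpoints and is silent on repeated testing over visits of the primary endpoint. Both sets of MSQOL-54 visit-level tests thus fall under the default 0.05 per test.

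The stake is how results are read after a non-significant Week 52. The p-values at Weeks 8, 24 and 42 will be in the tables. Nothing in the SAP labels them descriptive, and the protocol foresees using the data in reports, presentations and manuscripts. Because 5.4 states that nothing changed, a reader of the report would have no signal that the protocol's correction was not carried out on this endpoint.

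**Working it through.** **Inputs**

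- About 12 patients per arm: Protocol, Investigational Product Assignment.
- Two-sided 0.05 per test: SAP 5.1.1.
- Post-baseline MSQOL-54 visits: Protocol Table 4 schedules it at Visits 4, 6, 8 and 9, that is Weeks 8, 24, 42 and 52. The SAP lists seven weeks, but only these four have scheduled data, so I count four.
- Two composites, physical and mental: SAP 5.2.1.
- Correlations between visits and between composites: not given. I assume 0.5–0.85 and 0.4–0.8.

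**1. What the existing correction covers.** With the four endpoints of SAP 5.3.1, k = 4 and the Holm levels are 0.05/4 = 0.0125, 0.05/3 = 0.0167, 0.05/2 = 0.025 and 0.05. That controls the four-endpoint family at 0.05. No MSQOL-54 test is in it. The plan states no family-wise figure for the visit contrasts, so there is none to reproduce.

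**2. The event to measure.** The relevant event is: Week 52 non-significant, and at least one of the three earlier visits with p<0.05. Counting all four visits would mix in the error of Week 52 itself.

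**3. Reference under independence.**

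- One composite: 0.95 × (1 − 0.95³) = 0.95 × 0.1426 = 0.135.
- Both composites, both non-significant at Week 52: 0.95² × (1 − 0.95⁶) = 0.9025 × 0.2649 = 0.239.

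**4. With correlation.** I simulated 40,000 null trials per setting: 12 per arm, equal correlation between all visits, two-sample t-tests. Share of trials with the event in step 2:

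| Visit correlation | Composite correlation | One composite | Both composites |
|---|---|---|---|
| 0.5 | 0.4 | 10.9% | 18.8% |
| 0.5 | 0.8 | 10.6% | 15.8% |
| 0.7 | 0.4 | 8.3% | 14.4% |
| 0.7 | 0.8 | 8.3% | 12.3% |
| 0.85 | 0.4 | 5.7% | 10.0% |
| 0.85 | 0.8 | 5.8% | 8.7% |

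I quote these as about 6–11% and 8–19% (the lower end for both composites is rounded down).

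**5. What a correction would do.** When there is no effect anywhere, the error of Holm is set by its first step. For Weeks 8, 24 and 42:

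- Holm separately in each composite (k = 3, first level 0.05/3 = 0.0167) gives at least one false finding across the two composites in 5.6–8.6% of trials.
- One family over both composites (k = 3 × 2 = 6, first level 0.05/6 = 0.0083) gives 3.0–4.4%.

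Only the single family stays below 5% when both composites can support a finding.

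**6. Paired tests.** Four collected visits and two composites give 4 × 2 = 8 MSQOL-54 tests against baseline for each group analysed. Their p-values are also uncorrected.

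**The case against.** The strongest counter-argument concerns scope. The protocol sentence follows one about within-subject changes, so its most direct target is the baseline-to-visit comparisons. The between-arm contrasts are prespecified in the SAP and are not obviously post-hoc. This stands: a reader might infer an explicit promise to adjust the treatment-by-visit contrasts, or a promise of Holm in particular, and the protocol gives neither. It does not close the gap, because the paired tests, which fit the narrow reading best, are uncorrected too.

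Second, the SAP fixes its primary hypothesis at Week 52 and heads the visit analysis as secondary. Unadjusted secondary time points are common in a 24-patient phase 2 trial. This also stands. A reader might infer that the primary test is inflated, or that the SAP lets an early visit replace a failed Week 52. The documents say neither. What remains is that visit-level p-values will be reported without a statement of their status.

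Third, a reader might put the harm at 13% for one composite (visit correlation 0.7) and 16–28% for both. Those figures count any of four visits, including Week 52, and so overstate the early-visit harm. Setting a family rate against the per-test 0.05 is also not like for like, since the SAP states no family-wise rate for these contrasts.

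**Conclusion.** The point holds as an inconsistency between protocol and SAP with a moderate effect on visit-level findings. On the narrow reading of the protocol sentence (paired tests) and on the wider one (treatment contrasts), the SAP supplies no correction for MSQOL-54, and its statement in 5.4 is not accurate.

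The size of 6–11% for one composite and 8–19% for both rests on the assumed correlations, on 12 complete patients per arm, and on plain t-tests. The SAP's own model adjusts for baseline and strata and is fitted in patients who received all six infusions, so the exact figures would differ. The level of each Week 52 primary test does not change. Whether two composites at Week 52 need a joint decision rule is a separate question.

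**What to change.** - **SAP 3.1 and 5.2.2:** state that Week 52 is the only MSQOL-54 visit contrast used for an efficacy claim.
- **Weeks 8, 24 and 42:** either report estimates with 95% confidence intervals and no p-values, or apply Holm in one family across both composites, with k = 6 stated. This k counts only visits at which Table 4 schedules the instrument; the SAP's list of seven weeks should not be used to set it.
- **Paired tests in 5.2.2:** make the same choice, descriptive or corrected across visits and composites, with k stated.
- **SAP 5.4:** describe how the protocol's correction is carried out, or record that it has been changed and why.

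The cost is a few sentences in the SAP. The downside is that an early-visit difference can no longer be called significant at a nominal 0.05.

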### Derivation of MSQOL-54 Composite Scores

Two composite scores are defined for MSQOL-54 using the subscale scores defined in the table below. The MSQOL-54 Physical Health Composite score and the MSQOL-54 Mental Health Composite Scores are calculated as a weighted-sum using the subscale scores and the weights defined in table below. If a subscale score is missing then it will not contribute to the Composite Score calculation (in effect, it is treated as a score of 0).

Composite Score	Subscale	Weight for Composite
Physical Health	Physical Function	0.17
	Health Perceptions	0.17
	Energy	0.12
	Role Limitations - Physical	0.12
	Pain	0.11
	Sexual Function	0.08
	Social Function	0.12
	Health Distress	0.11
Mental Health	Health Distress	0.14
	Overall Quality of Life	0.18
	Emotional Well-being	0.29
	Role Limitations - Emotional	0.24
	Cognitive Function	0.15

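### The SAP makes two MSQOL-54 composites primary with no rule for success, and its sections disagree on the analysis model for the primary and secondary endpoints

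*SAP*

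**What the plan says.** **Primary endpoint.** SAP Section 3 gives one null and one alternative, on "The difference in change from baseline at Weeks 52 in Multiple Sclerosis Quality of Life (MSQOL)-54 Instrument scores between treatment groups". In Section 5.2.1 the SAP says: "Two composite scores are defined for MSQOL-54 using the subscale scores defined in the table below". These are Physical Health and Mental Health. Section 5.2.2 then takes as its primary variable "Change from baseline at Weeks 52 in Multiple Sclerosis Quality of Life (MSQOL)-54 Composite scores following treatment with HB-adMSCs or Placebo", in the plural, and names neither composite.

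**Significance level.** Section 5.1.1: "Unless otherwise stated, all hypotheses will be tested at a 2-sided significance level of 0.05". Section 3.1 confines Holm to the secondaries: "adjustment of multiplicity adjustment is performed for all secondary efficacy endpoint of interest". The protocol's one statement, under Statistical Methods, is that "correction for multiple comparisons will be employed for post-hoc comparisons".

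**Lead model for the secondaries.** Section 5.1.1: "As a primary analysis, a standard Analysis of Covariance (ANCOVA) will be applied for primary and secondary endpoint to test the significance". It gives the RMA a secondary role. Section 5.3.1 does the reverse for the same endpoints: RMA leads and ANCOVA follows.

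**Model terms.** The ANCOVA in Section 5.1.1 has treatment and baseline only. Section 5.2.2 adds disease severity, age and gender.

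**Visits.** The RMA in Section 5.2.2 names Weeks 4, 8, 16, 24, 32, 42 and 52. Protocol Table 4 schedules MSQOL-54, Barthel and the 9-Hole Peg Test (9-HPT) after baseline at Weeks 8, 24, 42 and 52 only. EDSS and PHQ-9 have one post-baseline assessment each, at Week 52.

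**PHQ-9.** The protocol objectives and SAP Section 2.1 place it under a safety objective. SAP Section 5.3.1 lists it among four efficacy endpoints.

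**The concern.** If exactly one composite reaches p < 0.05, the SAP supports calling the trial positive or negative, and the choice could be made after the data are seen.

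For the secondaries, two analysts who follow different sections would feed different p-values into Holm. For the primary, they could fit different ANCOVA models. The number of hypotheses in Holm, and whether the secondaries are tested only after a positive primary, are also left open. Each of these choices can change a reported conclusion, and none is fixed in advance.

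**Working it through.** **No plan figure to reproduce.** SAP Section 6 gives up to 24 subjects, with no effect size, SD, power or dropout. The inputs are two composites (5.2.1), two-sided 0.05 (5.1.1), and 1:1 allocation, so about 12 per arm (Protocol, Randomization and Blinding). Correlations and effect sizes below are assumptions. The composites share the Health Distress subscale (weights 0.11 and 0.14), so a positive correlation is likely.

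**1. False-claim rate with no effect on either composite.** With bivariate normal statistics and critical value 1.96, P(at least one) = 0.05 + 0.05 − P(both).

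| Correlation | P(both) | P(at least one) |
|---|---|---|
| 0 | 0.25% | 10 − 0.25 = 9.75% |
| 0.5 | 0.93% | 10 − 0.93 = 9.07% |
| 0.7 | 1.65% | 10 − 1.65 = 8.35% |
| 0.9 | 2.96% | 10 − 2.96 = 7.04% |

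When both are required, the error cannot exceed 5% even if one composite has a true effect, because the other must still pass at 0.05.

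**2. How often the missing rule decides the verdict.** This was simulated with 12 per arm and 24 − 6 = 18 residual df (intercept, treatment, baseline, three strata). Exactly one composite has p < 0.05 in 8.3%, 6.9% and 4.3% of trials with no effect (correlation 0.5, 0.7, 0.9). At an assumed 0.8 SD on both, the figures are 33.9%, 26.2% and 15.0%.

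**3. Lead model.** For EDSS and PHQ-9 the visit and treatment-by-visit terms drop out, because there is one post-baseline value. The RMA then equals the Week 52 ANCOVA with the same terms. For Barthel and 9-HPT the two can differ even with complete data, because the RMA has one baseline slope shared by all visits. The size depends on the covariance and on a degrees-of-freedom method that the SAP does not give, so no figure is put on it.

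**4. Strata.** This conflict is separate and wider. Under 5.1.1 a Week 52 ANCOVA has 24 − 3 = 21 residual df; under 5.2.2 it has 18. It affects the primary, EDSS and PHQ-9 as well. In simulation (12 per arm, assumed 0.8 SD), the p < 0.05 verdict changes in about 5% of trials even when the strata are balanced and not prognostic.

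**5. Holm's first step.** With k = 4 it is 5/4 = 1.25%; with k = 3 (PHQ-9 treated as safety) it is 5/3 = 1.67%.

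**6. Visits.** Weeks 4, 16 and 32 are Visits 3, 5 and 7. Table 4 and the list of disease-activity visits in the Investigational Plan both omit them for these scores.

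**The case against.** **Only one hypothesis is stated, so there is no multiplicity.** The hypothesis never says which score it concerns, so it supplies no rule.

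**Specific text overrides general text.** A statistician may well follow 5.2.2 for the primary and 5.3.1 for the secondaries. That is a sensible reading, but the ANCOVA statement in 5.1.1 names the secondary endpoints outright and yields to nothing. Section 5.4 does not settle the order either.

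**This is a 24-subject phase 2 trial with no power target.** That is true, and it limits the severity. It does not remove the need for a rule when the SAP sets out a superiority test.

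**Stronger readings that the documents do not support.**
- A reader might infer that the primary error is inflated to nearly 10%. That follows only if either composite suffices, which the SAP does not say.
- A reader might infer that the ANCOVA/RMA reversal alters all four secondaries. In itself it matters for Barthel and 9-HPT; EDSS and PHQ-9 are touched by the strata conflict.
- A reader might take the protocol to settle the lead model, since it says "A repeat measure mixed model will be used to assess within-subject changes from baseline". That concerns change within subjects, not the contrast between arms at Week 52.
- A reader might add the stratum boundaries. The protocol's age strata have no gap, and the inequality signs in the SAP may be a loss in text conversion. EDSS 6.5 is eligible but in neither protocol severity stratum. That is a separate matter, which SAP wording alone cannot repair.

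**Conclusion.** The point holds as a missing rule and a set of contradictions. Depending on a rule not yet written, the same primary analysis has a false-claim rate of at most 5%, or of 7.0% to 9.75% over assumed correlations 0.9 to 0. The rule would decide the verdict in about 4% to 8% of trials with no effect, and in 15% to 34% at an assumed 0.8 SD on both composites (correlation 0.9 to 0.5).

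The reversed lead model, the omitted strata, the unscheduled RMA visits and the uncertain k are plain in the text and rest on no assumption. The strata conflict is substantive rather than a matter of wording, because it reaches the primary endpoint. The sponsor should correct these items before unblinding.

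**What to change.** Amend the SAP before unblinding:

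1. **Primary rule.** In Section 3, name both composites and test them by Holm at overall two-sided 0.05: the smaller p against 0.025, then the other against 0.05. Alternatives are to name one composite, or to require both at 0.05.
2. **Model.** State the same lead analysis for the secondaries in 5.1.1 and 5.3.1, either the RMA Week 52 contrast or ANCOVA. Put the 5.2.2 terms, including the stratification factors, into 5.1.1 for primary and secondaries. Say that the model uses the stratum actually used at randomization.
3. **Holm for the secondaries.** State that it takes the Week 52 p-values from the lead analysis, with k = 4 if PHQ-9 stays an efficacy endpoint and k = 3 otherwise. State whether it is gated on the primary. If ungated, the error across the two Holm families is bounded by 5% + 5% = 10%, and the SAP should say so.
4. **Visits.** Limit the RMA to Weeks 8, 24, 42 and 52 for MSQOL-54, Barthel and 9-HPT.

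**Cost.** These are SAP wording changes and need no new data. Holm on the primary costs power. By the noncentral t with 18 df and noncentrality d√(12/2), the difference detectable with 80% power at the first step rises from about 1.21 to 1.35 residual SD. With 10 per arm it rises from 1.35 to 1.52, and with 8 from 1.56 to 1.77. The smaller arms are assumed, since the efficacy set admits only those who received all six infusions. Naming one composite gives up a claim on the other. Requiring both lowers power at an assumed 1.0 SD from 64% for one composite to between 48% and 57% (correlation 0.5 to 0.9). Gating on both composites keeps overall error at 5%, but the secondaries would then be tested in only 27% to 35% of trials at an assumed 0.8 SD.
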